### 7.12.2 Central Laboratory

Blood samples must be drawn for the central determination of:

- HbA1c at Visits 2 – Baseline, 3 – Middle of parallel phase, 4 – End of parallel phase, and 5 –Final visit

For details regarding tubes, labelling, packaging, dispatch to central laboratory, please refer to the Central Laboratory Handbook.

Name of Central Laboratory    Q Squared Solutions Ltd.  
Address                            [name]  
    [name]  
    United Kingdom

### 7.13 Data Collection

A **Subject Identification Log** will be completed for all subjects who have provided their informed consent i.e., signed the Subject Informed Consent Form.

#### eCRF

An eCRF has been set up for this study.

For each subject who has signed the Subject Informed Consent Form, the Investigator must allocate a **subject ID number** via the eCRF-system of two digits for the site and three digits for the subject: **SS-XXX**.

For each enrolled subject, an eCRF must be completed (throughout the study) and electronically signed by the Principal Investigator or Sub-/ Co-Investigator (at the end of the subject's participation in the study).

Upon training, Investigators and authorized study staff will enter subject data during or shortly after the respective visits.

#### Data Discrepancy Management

Subsequently, the entered data will be systematically checked:

- by means of pre-defined computerized validation checks (as outlined in the Data Management Plan)
- by data review by the Sponsor including but not limited to the Data Manager, Monitor and Study Manager.

All data discrepancies will result in data queries within the eCRF-system, which must be addressed (data confirmed or changed) by the study site staff and closed by the originator.

In addition, protocol deviations must be recorded throughout the study and documented further, as applicable (see section 14).

If a subject withdraws from the study, the reason must be recorded on the eCRF.

#### Subject Questionnaires

Subjects will be asked to complete a set of questionnaires at each visit, see section 7.10. These questionnaires will be presented electronically.

Upon completion of the questionnaires, the subject will press "Save" and close the document. This enables entries to be saved (in the eCRF). This will generate a notification to (named) study staff that the questionnaires have been completed/saved.

For the sake of confidentiality, neither the Investigator nor other study staff will be able to read the subject's entries.

### **Database Closure**

Quality control of the database will be made throughout the study conduct in order to prepare the database closure. After the database has been declared clean (i.e. complete and accurate), the database will be locked.

Any changes to the database after that time can only be made by joint written agreement between the Study Manager and the Statistician.

## **7.14 Medical Care after Study Participation**

Upon the subject's planned termination in the clinical study, it is up to the subject him/herself, preferably in agreement with the treating physician, for the future treatment

- to return to the device used prior to the study or
- to continue with the investigational device, if CE-mark has been obtained or
- to use any other suitable device available on the market.

## **8 Risk/Benefit Analysis of the Investigational Device and Clinical Investigation**

### **8.1 Potential Risks**

During participation in this clinical study, subjects may encounter the following known potential risks of insulin pump therapy:

- Possible hypoglycemia.
- Possible hyperglycemia which might progress to ketosis and diabetic ketoacidosis (DKA)
- Infusion site reactions (bleeding, bruising, inflammation, infection, etc.)

The above risks are an integral part of intensive insulin therapy and applied in daily practice. It has to be underlined that subjects face the same risks as listed during their routine therapy. The likelihood of serious events occurring is considered uncommon.

### **8.2 Minimization of Risks**

The Sponsor has minimized the potential of the above risks to occur by:

- Selection of qualified investigators consulting study subjects during the scheduled visits including an inspection of infusion sites.
- Selection of subjects experienced in MDI therapy lacking any serious problems regarding the risks mentioned above.
- Selecting subjects adhering to the minimum number of 4 blood glucose measurements per day recommended for MDI therapy.
- Design of the clinical study, including individualized training which will include the precautions for pump systems e.g., to measure blood glucose 1-3 hours after insertion device / cannula (see instructions for use), if applicable.
- Subjects are advised not to change their current diabetes therapy without consulting their physician (Investigator), if applicable.

Furthermore, a risk analysis was performed, resulting measures have been implemented and none of the remaining risks is outside the acceptable region (Reference: Risk Management, Roche on file).

### **8.3 Potential Benefits**

The study subjects may experience the following potential benefits while participating in this study:

- mylife™ OmniPod® system and the Accu-Chek® Solo micropump system will be provided at no charge to subjects.
- Screening and study visits (as well as scheduled telephone calls) will be provided at no charge to subjects.
- Study subjects will gain additional attention by their physician.
- Subjects may be motivated to learn more about diabetes and to have better discussions of potential issues with their health care providers.
- Subjects may gain personal satisfaction from participating in this study.
- Subjects may experience improved treatment satisfaction from participating in this study, which might increase therapy adherence and thus reduce their HbA1c.

CONFIDENTIAL

## **9 Adverse Events Recording and Reporting**

The definitions are based on ISO 14155:2011(E) and respective sections CFR Title 21 for Medical Device Studies.

### **9.1.1 Adverse Event**

An Adverse Event (AE) is any untoward medical occurrence, unintended disease or injury, or untoward clinical signs (including abnormal laboratory findings) in subjects, users or other persons, whether or not related to the investigational medical device.

In addition, this definition includes events related to the procedures involved. For users or other persons, this definition is restricted to events related to investigational medical devices.

### **9.1.2 Serious Adverse Event**

A Serious Adverse Event (SAE) is any AE that fulfils at least one of the following criteria:

- Led to death.
- Led to a serious deterioration in the health of a subject resulting in:
  - A life-threatening illness or injury, or
  - A permanent impairment of a body structure or a body function, or
  - An in-patient or prolonged hospitalization, or
  - A medical or surgical intervention to prevent life-threatening illness or injury or permanent impairment to a body structure or a body function.
- Fetal distress, fetal death or a congenital abnormality or birth defect.

A planned hospitalization for a pre-existing condition, or a procedure required by the study procedure, without serious deterioration in health, is not considered an SAE.

Applicable for Germany only:

Serious Adverse Event (SAE) definition according to MPSV:

A serious adverse event is defined by German Ordinance on the Medical Device Safety Plan (MPSV) as any untoward medical event in a clinical trial or performance evaluation, which is subject to approval, that directly or indirectly led, could have led or could lead to death, or resulted, could have resulted or could result in a serious deterioration of health status or death of a subject, user or another person, whether or not related to the investigational medical device.

### **9.1.3 Adverse Device Effects**

An Adverse Device Effect (ADE) is any untoward medical occurrence, unintended disease or injury, or untoward clinical signs (including abnormal laboratory findings) in subjects, users or other persons related to the use of an investigational medical device (including consumables).

NOTE: This definition includes adverse events resulting from insufficient or inadequate instructions for use, deployment, implantation, installation, or operation, or any malfunction of the investigational medical device.

NOTE: This definition includes any event resulting from use error or from intentional misuse of the investigational medical device.

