## Protocol Outline

For comprehensive details, please refer to the respective sections.

Study Title:	Patient-Reported Outcomes with the Accu-Chek® Solo Micropump System vs. Multiple Daily Injection Therapy vs. mylife OmniPod® in People with Type 1 Diabetes
Short Name	PRO Solo Study
Investigational Device:	Accu-Chek® Solo micropump system
Other Study Devices:	
 
- Intensified therapy with multiple daily injections (MDI)
 
- mylife™ OmniPod® Insulin Management System (Insulet Corporation)
 

Research Question/ Working Hypothesis:	
Assessment of treatment satisfaction in patients with type 1 diabetes comparing Accu-Chek® Solo to standard therapy via MDI and to mylife™ OmniPod®.
 
First Null hypothesis: There is no difference in treatment satisfaction between Accu-Chek® Solo and MDI.
 
First Alternative hypothesis: Treatment satisfaction is higher with Accu-Chek® Solo than with MDI.
 
Second Null hypothesis: There is no difference in treatment satisfaction between Accu-Chek® Solo and mylife™ OmniPod®.
 
Second Alternative hypothesis: Treatment satisfaction is higher with Accu-Chek® Solo than with mylife™ OmniPod®.

Primary Objective:	To compare treatment satisfaction with Accu-Chek® Solo versus MDI and versus mylife™ OmniPod® assessed by Diabetes Technology Questionnaire (DTQ).
Secondary Objectives:	
To evaluate
 
 
• Mean HbA1c change difference between treatment groups at end of study
 
• Therapy relevant examination and diary parameters
 
• The answers of additional questionnaires measuring psychological parameters relevant in diabetes therapy
 
• Therapy relevant parameters from data download from BG-meter or respective patch pump, e.g. bolus frequency
 
• Device parameters
 

Indication	Type 1 diabetes mellitus
Target Population	Age ≥ 18 years
Number of Subjects	180 subjects, 60 subjects in each treatment group
Number of Sites	10-20
Countries	Austria, Germany, Poland, and UK
Study Design:	
Prospective, multinational study where adults ≥ 18 years will be randomly allocated (1:1:1 ratio) to
 
Group A: Continuous subcutaneous insulin infusion (CSII) with Accu-Chek® Solo micropump system for 26 weeks.
 
or

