### 3 Study Device(s)

#### 3.1 Identification and Description of the Investigational Device: Accu-Chek® Solo micropump system

The Accu-Chek® Solo micropump system is a medical device for subcutaneous delivery of insulin in a personalized way. It is characterized by a high degree of miniaturization and modularity. The Accu-Chek® Solo micropump system consists of two main parts: the Accu-Chek® Solo micropump and Accu-Chek® Aviva/Performa Solo Diabetes Manager that integrates all therapy data and acts as remote control of the actual micropump.

Figure 2: Accu-Chek® Solo Aviva Diabetes Manager (left) and Accu-Chek® Solo micropump (right)

The Diabetes Manager is a key component of the system that communicates with the micropump via Bluetooth Low Energy. It controls the pump and displays all operational information from the pump. All interaction with the pump except the final confirmation of insulin doses is done via the Diabetes Manager's interactive touch screen. The Diabetes Manager features a hardware button that is used specifically to confirm insulin doses. In addition, it includes an Accu-Chek® Aviva/Performa blood glucose meter with integrated bolus advisor functionality.

The Accu-Chek® Solo micropump delivers insulin as programmed via the Diabetes Manager. Furthermore, it features two buttons directly on the micropump, enabling users to program a bolus on demand without the Diabetes Manager. The pump stores parameters such as the activated basal rate profile and the bolus button increment. Therefore, basic basal-bolus therapy is available even when the Diabetes Manager is not present or when communication between the devices is not available.

[figure not shown]

Figure 3: Accu-Chek® Solo pump base (left), Accu-Chek® Solo reservoir (middle), Accu-Chek® Solo reservoir assembly

The micropump actually consists of a pump base, and a disposable reservoir:

The pump base (Accu-Chek® micropump base) has a lifetime of 120 days and contains electronics, memory, pump engine, bolus buttons as well as a buzzer to inform the user in case of pump events.

The disposable reservoir integrates a button cell and an insulin compartment holding up to 2 ml of insulin (i.e. 200 units of U100 insulin) with a minimum filling amount of corresponding to 80 units. The reservoir is provided as part of a reservoir assembly that enables the user to fill the insulin compartment directly from 10 ml vials. The filling aid is not reusable.

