### **3.2 Comparator Devices: mylife™ OmniPod® Insulin Management System and Other Study Devices**

#### **3.2.1 Multiple daily injection therapy**

Intensified therapy, either MDI or CSII, strongly depends on multiple self-monitored blood glucose values. Both the mylife™ OmniPod® and the Accu-Chek® Solo micropump system offer an integrated blood glucose meter. Accordingly, subjects on CSII therapy will use the meter integrated into the respective pump system. Subjects in the MDI control arm will use either a blood glucometer of their own choice, if this is listed as a compatible meter with Accu-Chek® Smart Pix or will switch to a provided Accu-Chek® Aviva/Performa Connect or Accu-Chek® Aviva/Performa Nano as blood glucose meter for the duration of the study. No effect is expected by the specific brand or model of blood glucose meter.

Figure 5: Accu-Chek® blood glucose meters

Subjects in group A will use either a Smart Pix compatible blood glucometer of their own choice or the depicted device (Accu-Chek® Aviva/Performa Connect, left or Accu-Chek® Aviva/Performa Nano, right) for 26 weeks.

MDI therapy has been chosen as comparator, as it is standard of care.

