#### **9.1.4 Serious Adverse Device Effects**

A Serious Adverse Device Effect (SADE) is any adverse device effect that has resulted in any of the consequences characteristic of a Serious Adverse Event.

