### 10.2 Incident Reporting

The Investigators should identify incidents with direct and indirect harms of devices with CE-mark used within Intended Use (as defined in the beginning of this section), and report such on the **Incidents Report** (integrated into the eCRF) which should be sent to the Sponsor immediately.

Even if the requested information is not yet complete, it is required to submit the report immediately.

Respective contact details can be found in the Investigator site file and in the Incident Report in the eCRF.

Subjects will report such incidents to the respective Call Centre, as usual for these products or inform their Investigator. Contact details will be noted on subject's identification card.

In case of doubt on the duty to report an incident, there should be a pre-disposition to report rather than not to report - as a general principle

Incidents with devices from other manufacturers should be reported directly to the respective manufacturer.

CONFIDENTIAL

Identified malfunctions will be submitted to the Sponsor – either via the eCRF or by means of a separate **Malfunction Report**.

In addition, all incidents and indirect harms are also to be documented in the source data. The following details should be provided:

- Description of event/incident
- Start date
- Resolution date
- Action taken
- Outcome

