## 11.7 Safety Analysis

All AEs will be coded using the Medical Dictionary for Regulatory Activities (MedDRA). Only AEs occurring after the start of the treatment with either MDI, mylife™ Omnipod® or Accu-Chek® Solo micropump system will be included in the AEs tables.

Summaries of incidence rates (frequencies and percentages) of individual AEs by MedDRA System Organ Class and Preferred Term will be prepared. Such summaries will be displayed for all AEs, AEs by maximum severity, AEs by strongest causality to study device (and any associated pump devices), and AEs leading to withdrawal of study device.

Deaths, other SAEs and AEs leading to withdrawal will be listed separately.

In addition, the sub-group of ADEs and SADEs will also be summarized by MedDRA System Organ Class and Preferred Term including summaries by study device.

Episodes (numbers) of the following AEs will be summarized:

- Symptomatic hypoglycemia
- Severe hypoglycemia (SAEs)
- Diabetic Ketoacidosis (SAEs)

The following ADEs are of particular interest:

- ADEs leading to replacement of device.

Incidence rates of all ADEs and of these ADEs and AEs of special interest (as captured on the AE Form in the eCRF) per 100 patient years will be calculated together with exact two-sided 95% CIs assuming that the number of special AEs observed in the study is Poisson distributed.

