### 6.12. Evaluation of Safety Variables

The safety analysis will be based on the SP and on the device, a subject is using at the time, when a safety event occurs. Since all subjects in treatment arms B and C will receive an Accu-Chek® Solo micropump system at Visit 4 (week 26) and will use it until the end of the study, AEs and SAEs occurring at or after Visit 4 will be attributed to the Accu-Chek® Solo micropump

system. Distinction will be handled and documented according to the description in section 6.2.1.

All AEs will be coded using the Medical Dictionary for Regulatory Activities (MedDRA). Summaries of incidence rates of overall AEs and of individual AEs by MedDRA system Organ Class and Preferred Term will be prepared. Furthermore, summaries will be tabulated for all AEs, AEs by maximum severity, AEs by strongest causality to study device.

Summaries will include number of events, number of subjects affected, the percentages of all subjects for a given treatment, and the events per year of use for a given device.

Defective devices will be tabulated and listed by device type and treatment arm.

Deaths, SAEs and AEs leading to withdrawal will be listed separately.

Episodes (numbers) of the following AEs will be summarized:

- Symptomatic hypoglycemia
- Severe hypoglycemia (SAEs)
- Diabetic Ketoacidosis (SAEs)

The following ADEs are of particular interest:

- ADEs leading to replacement of device.

Incidence rates of all ADEs and of these ADEs and AEs of special interest (as captured on the AE Form in the eCRF) per 100 patient years will be calculated together with exact two-sided 95% CIs assuming that the number of special AEs observed in the study is Poisson distributed.

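### Adverse device effects are defined only for the investigational device (Solo) but summarised by study device, so the ADE and SADE figures cannot be compared between the two pumps

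*Protocol*

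**What the plan says.** Protocol 9.1.3 defines an ADE as an untoward occurrence "in subjects, users or other persons related to the use of an investigational medical device (including consumables"). Its two notes, on malfunction and on use error, also refer to the investigational device. Protocol 9.1.4 adds: "A Serious Adverse Device Effect (SADE) is any adverse device effect that has resulted in any of the consequences characteristic of a Serious Adverse Event".

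The Protocol Outline lists Solo as the investigational device, with MDI and OmniPod under other study devices. The heading of section 3.1 reads "Identification and Description of the Investigational Device: Accu-Chek® Solo micropump system" and that of section 3.2 reads "Comparator Devices: mylife™ OmniPod® Insulin Management System and Other Study Devices".

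On outputs, Protocol 11.7 says that "the sub-group of ADEs and SADEs will also be summarized by MedDRA System Organ Class and Preferred Term including summaries by study device". SAP 6.12 organises the safety analysis by the device in use when the event occurs and plans "Incidence rates of all ADEs and of these ADEs and AEs of special interest (as captured on the AE Form in the eCRF) per 100" patient-years, with exact Poisson 95% intervals. The SAP gives no ADE definition of its own.

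On incidents, Protocol 10.2 first asks investigators to report incidents with CE-marked devices to the sponsor through the eCRF. Later it says: "Incidents with devices from other manufacturers should be reported directly to the respective manufacturer".

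**The concern.** The definition covers one device, while the tables built on it are laid out for all of them. A plaster reaction under an OmniPod pod and the same reaction under a Solo pump holder are both adverse events, but under 9.1.3 as worded only the second can be an ADE. The same limit applies to the MDI arm.

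Solo against OmniPod is a randomised comparison in this trial, so readers will set the two columns side by side. An OmniPod rate of zero with a confidence interval looks like an observation. Here it would follow from the definition and would count against the sponsor's own device. If some sites apply the wider sense of the term and others the narrow one, the figure becomes a mixture with no clear meaning.

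**Working it through.** The plan states no ADE rate, so there is no figure to reproduce. The check has two parts.

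**1. Reading the definitions together**

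- *Is Solo the only investigational device?* The outline and sections 3.1 and 3.2 say so. Protocol 7.14 agrees: after the study a subject may stay on the investigational device if it has obtained its CE mark. That condition fits only Solo, because Table 1 in section 3.3 shows OmniPod as CE-marked at study start.
- *Does anything widen the ADE definition for analysis?* Nothing does so explicitly. Protocol 9.4 rates causality against a device in general, and 9.6 speaks of study devices, but neither redefines an ADE.
- *Do the outputs assume the wider sense?* Protocol 11.7 does for the ADE and SADE summaries, since a split by study device has little purpose if only one device can contribute. The sentence on rates per 100 patient-years names no split itself. It sits in SAP 6.12, whose opening rule is device in use.

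The two readings give different tables, and neither document tells a site or programmer which to use.

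**2. Size of the effect on the OmniPod rate**

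Inputs: 60 subjects per arm (Protocol 11.1); 26 weeks on OmniPod (3.2.2); 39 weeks on Solo in group A and 13 weeks in groups B and C (2.1); exact Poisson intervals (11.7, SAP 6.12). Full retention is assumed.

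- Patient-years = subjects × weeks × 7 / 365.25.
- OmniPod: 60 × 26 × 7 / 365.25 = 29.9.
- Solo, counted by device in use: (60 × 39 + 120 × 13) × 7 / 365.25 = 3,900 × 7 / 365.25 = 74.7.
- Exact limits for x events over T patient-years: lower = χ²(0.025; 2x) / (2T), upper = χ²(0.975; 2x + 2) / (2T). For x = 0 the lower limit is 0 and the upper is 3.689 / T.
- OmniPod with x = 0: rate 0, upper limit 3.689 / 29.9 = 12.3 per 100 patient-years.
- With only the 49 evaluable subjects per arm, T = 24.4 and the upper limit is 15.1.

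The documents give no expected number of OmniPod-related events. The table shows what the zero would replace under assumed counts, at 60 subjects:

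| OmniPod-related events (assumed) | Rate per 100 patient-years | Exact 95% CI | Shown under the literal definition |
|---|---|---|---|
| 3 | 10.0 | 2.1 to 29.3 | 0 (0 to 12.3) |
| 6 | 20.1 | 7.4 to 43.7 | 0 (0 to 12.3) |
| 10 | 33.4 | 16.0 to 61.5 | 0 (0 to 12.3) |

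**The case against.** The strongest reply is that OmniPod harm is well documented elsewhere, and this is correct. Adverse events are recorded whether or not they relate to the investigational device (9.1.1). The captured events in 9.3.1.1, such as site infection, plaster reactions and hyperglycaemia suspected to come from leakage or occlusion, are not restricted to Solo. Protocol 11.7 tabulates events by strongest causality to the study device and associated pump devices. SAP 6.12 gives adverse events per year of use of each device and tabulates defective devices by type and arm. Insertion-site findings are tabulated by treatment group and visit (SAP 6.8.1.4). A reader might infer that OmniPod will look free of device harm throughout the report. The documents do not support that: only the ADE and SADE labels are affected.

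Second, the zero is not certain in practice. The protocol uses the plural, investigational devices, loosely in 6.1, 13.1.2, 13.1.4 and 13.5, and the by-device split in 11.7 suggests that a wider sense was meant. This stands. It turns a certain zero into either a zero or inconsistent coding, and neither allows a comparison.

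Third, a reader might infer that the incident route in 10.2 produces the zero. It does not. Incident reporting is separate from adverse event recording and removes nothing from the AE form. Section 10.2 also points both ways for OmniPod, which is CE-marked and made by another manufacturer. Malfunctions of any study device go to the sponsor, incidents must be documented in source data, and no incident-rate comparison is planned.

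Finally, safety is not a primary endpoint (2.2), no between-device ADE test is planned, and the device-specific secondary parameters in 4.2 do not depend on the ADE definition. This limits the importance of the point but does not make the planned table interpretable.

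**Conclusion.** The point holds, confined to the ADE and SADE tables and rates. As worded, 9.1.3 and 9.1.4 give OmniPod a structural zero in outputs that 11.7 splits by study device and SAP 6.12 treats by device in use. The printed result would be 0 per 100 patient-years (exact 95% CI 0 to 12.3) over about 29.9 patient-years, or 0 to 15.1 with 49 subjects. This assumes 26 weeks of exposure for every counted subject and the literal reading. Under the looser reading the harm is uneven coding between sites, which cannot be sized from the documents.

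This is more than a missing detail, because a stated rule, if followed, gives a misleading figure. It does not show that Solo will appear worse by any particular amount. That would need true event rates, which the documents do not give, and a comparison over 30 patient-years on each pump would not match the SAP, under which Solo accrues about 74.7. The primary endpoint is unaffected.

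**What to change.** Add one derivation rule to SAP 6.12 and Protocol 11.7. For analysis, an ADE or SADE is an AE or SAE rated related or possibly related to any study device in use (Solo, OmniPod or MDI device, including consumables). The rule should also say how events rated not assessable (9.4.4) are counted. Keep the 9.1.3 definition for regulatory reporting.

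If the sponsor prefers not to widen the term, label the ADE and SADE tables and rates as Solo-only and compare devices on the AE-by-causality table. In that case carry the reference to associated pump devices from Protocol 11.7 into SAP 6.12, where it is absent.

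Separately, reconcile the two sentences in 10.2 so that an OmniPod incident reported to its manufacturer is also recorded in the eCRF.

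The cost is low: wording in two documents, a short note to sites and a few lines of programming. Causality is already rated for every recorded event, so the ADE tables need no new data provided the rating can be linked to the device in use. The incident change adds one eCRF entry per OmniPod incident.
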